7.1.2 Visit 2 – run-in period (day -14±3)

- Confirm eligibility
- Diet and exercise counseling
- Glucometer dispensing and training for SMBG determination
- Discontinue anti-diabetic medication
- Vital Signs: blood pressure, pulse, temperature, respiratory rate taken in the sitting position after at least 5 minutes of rest. Blood pressure must be measured twice with at least 3 min apart

Dispense study medication for the run-in period

7.2 Primary Efficacy Phase

7.2.1 Visit 3 – procedures (Day 1 in Week 0)

- The subject must be queried to assess compliance with a minimum of a 10 h fast prior to blood draw to ensure the FPG values can be accurately determined. Only water is permitted. If a subject has not fasted for 10 h, the subject should return within a week after proper fasting.
- Confirm eligibility
- Diary and SMBG review
- Adverse events and pre-treatment medications assessment
- Randomization
- Vital Signs: blood pressure, pulse, temperature, respiratory rate taken in the sitting position after at least 5 minutes of rest. Blood pressure must be measured twice with at least 3 min apart
- 12 lead ECG taken in the supine position after at least 5 minutes of rest
- Dispense study medication based on randomization assignment
- Blood draw for hematology (CBC with platelets, WBC with differential), serum chemistry including FPG, and coagulation as detailed in section 6.7.1
- Urinalysis

7.2.2 Visit 4 – Procedures (week 2)

- The subject must be queried to assess compliance with a minimum of a 10 h fast prior to blood draw to ensure the FPG values can be accurately determined. Only water is permitted. If a subject has not fasted for 10 h, the subject should return within a week after proper fasting.
- Diary and SMBG review
- Vital Signs: blood pressure, pulse, temperature, respiratory rate taken in the sitting position after at least 5 minutes of rest. Blood pressure must be measured twice with at least 3 min apart
- Blood draw for hematology (CBC with platelets, WBC with differential), serum chemistry including FPG, and coagulation as detailed in section 6.7.1
- Urinalysis

- Collect plasma sample for drug exposure verification
- Assess adverse events and record concomitant medications

7.2.3 Visit 5 – Procedures (week 6)

- The subject must be queried to assess compliance with a minimum of a 10 h fast prior to blood draw to ensure the FPG values can be accurately determined. Only water is permitted. If a subject has not fasted for 10 h, the subject should return within a week after proper fasting.
- Diary and SMBG review
- Vital Signs: blood pressure, pulse, temperature, respiratory rate taken in the sitting position after at least 5 minutes of rest. Blood pressure must be measured twice with at least 3 min apart
- Dispense study medication
- Blood draw for hematology (CBC with platelets, WBC with differential), serum chemistry including FPG, and coagulation as detailed in section 6.7.1
- Urinalysis
- Collect plasma sample for drug exposure verification
- Assess adverse events and record concomitant medications

7.2.4 Visit 6 – Procedures (week 12)

- The subject must be queried to assess compliance with a minimum of a 10 h fast prior to blood draw to ensure the FPG values can be accurately determined. Only water is permitted. If a subject has not fasted for 10 h, the subject should return within a week after proper fasting.
- Diary and SMBG review
- Diet and exercise counseling
- Physical examination
- Vital Signs: blood pressure, pulse, temperature, respiratory rate taken in the sitting position after at least 5 minutes of rest. Blood pressure must be measured twice with at least 3 min apart
- Dispense study medication
- Blood draw for hematology (CBC with platelets, WBC with differential), serum chemistry including FPG, and coagulation as detailed in section 6.7.1

- Urinalysis
- Collect plasma sample for drug exposure verification
- Assess adverse events and record concomitant medications

7.2.5 Visit 7 – Procedures (week 18)

- The subject must be queried to assess compliance with a minimum of a 10 h fast prior to blood draw to ensure the FPG values can be accurately determined. Only water is permitted. If a subject has not fasted for 10 h, the subject should return within a week after proper fasting.
- Diary and SMBG review
- Vital Signs: blood pressure, pulse, temperature, respiratory rate taken in the sitting position after at least 5 minutes of rest. Blood pressure must be measured twice with at least 3 min apart
- Dispense study medication
- Blood draw for hematology (CBC with platelets, WBC with differential), serum chemistry including FPG, and coagulation as detailed in section 6.7.1
- Urinalysis
- Collect plasma sample for drug exposure verification
- Assess adverse events and record concomitant medications

7.2.6 Visit 8 – Procedures (week 24)

- The subject must be queried to assess compliance with a minimum of a 10 h fast prior to blood draw to ensure the FPG values can be accurately determined. Only water is permitted. If a subject has not fasted for 10 h, the subject should return within a week after proper fasting.
- Diary and SMBG review
- Diet and exercise counseling
- Physical examination
- Vital Signs: blood pressure, pulse, temperature, respiratory rate taken in the sitting position after at least 5 minutes of rest. Blood pressure must be measured twice with at least 3 min apart
- 12 lead ECG taken in the supine position after at least 5 minutes of rest
- Dispense study medication

- Blood draw for hematology (CBC with platelets, WBC with differential), serum chemistry including FPG, and coagulation as detailed in section 6.7.1
- Urinalysis
- Collect plasma sample for drug exposure verification
- Assess adverse events and record concomitant medications

7.3 Extension Phase

7.3.1 Visit 9 – Procedures (week 36)

- The subject must be queried to assess compliance with a minimum of a 10 h fast prior to blood draw to ensure the FPG values can be accurately determined. Only water is permitted. If a subject has not fasted for 10 h, the subject should return within a week after proper fasting.
- Diary and SMBG review
- Vital Signs: blood pressure, pulse, temperature, respiratory rate taken in the sitting position after at least 5 minutes of rest. Blood pressure must be measured twice with at least 3 min apart
- Dispense study medication
- Blood draw for hematology (CBC with platelets, WBC with differential), serum chemistry including FPG, and coagulation as detailed in section 6.7.1
- Urinalysis
- Collect plasma sample for drug exposure verification
- Assess adverse events and record concomitant medications

7.3.2 Visit 10 – Procedures (week 48)

- The subject must be queried to assess compliance with a minimum of a 10 h fast prior to blood draw to ensure the FPG values can be accurately determined. Only water is permitted. If a subject has not fasted for 10 h, the subject should return within a week after proper fasting.
- Diary and SMBG review
- Diet and exercise counseling
- Physical examination

- Vital Signs: blood pressure, pulse, temperature, respiratory rate taken in the sitting position after at least 5 minutes of rest. Blood pressure must be measured twice with at least 3 min apart
- Dispense study medication
- Blood draw for hematology (CBC with platelets, WBC with differential), serum chemistry including FPG, and coagulation as detailed in section 6.7.1
- Urinalysis
- Collect plasma sample for drug exposure verification
- Assess adverse events and record concomitant medications

7.3.3 Visit 11 – Procedures (week 60)

- The subject must be queried to assess compliance with a minimum of a 10 h fast prior to blood draw to ensure the FPG values can be accurately determined. Only water is permitted. If a subject has not fasted for 10 h, the subject should return within a week after proper fasting.
- Diary and SMBG review
- Vital Signs: blood pressure, pulse, temperature, respiratory rate taken in the sitting position after at least 5 minutes of rest. Blood pressure must be measured twice with at least 3 min apart
- 12 lead ECG taken in the supine position after at least 5 minutes of rest
- Dispense study medication
- Blood draw for hematology (CBC with platelets, WBC with differential), serum chemistry including FPG, and coagulation as detailed in section 6.7.1
- Urinalysis
- Collect plasma sample for drug exposure verification
- Assess adverse events and record concomitant medications

7.3.4 Visit 12 – Procedures (week 72)

• The subject must be queried to assess compliance with a minimum of a 10 h fast prior to blood draw to ensure the FPG values can be accurately determined. Only water is permitted. If a subject has not fasted for 10 h, the subject should return within a week after proper fasting.

- Diary and SMBG review
- Diet and exercise counseling
- Physical examination
- Vital Signs: blood pressure, pulse, temperature, respiratory rate taken in the sitting position after at least 5 minutes of rest. Blood pressure must be measured twice with at least 3 min apart
- Dispense study medication
- Blood draw for hematology (CBC with platelets, WBC with differential), serum chemistry including FPG, and coagulation as detailed in section 6.7.1
- Urinalysis
- Collect plasma sample for drug exposure verification
- Assess adverse events and record concomitant medications

7.3.5 Visit 13 – Procedures (week 84)

- The subject must be queried to assess compliance with a minimum of a 10 h fast prior to blood draw to ensure the FPG values can be accurately determined. Only water is permitted. If a subject has not fasted for 10 h, the subject should return within a week after proper fasting.
- Diary and SMBG review
- Vital Signs: blood pressure, pulse, temperature, respiratory rate taken in the sitting position after at least 5 minutes of rest. Blood pressure must be measured twice with at least 3 min apart
- Dispense study medication
- Blood draw for hematology (CBC with platelets, WBC with differential), serum chemistry including FPG, and coagulation as detailed in section 6.7.1
- Urinalysis
- Collect plasma sample for drug exposure verification
- Assess adverse events and record concomitant medications

7.3.6 Visit 14 – Procedures (week 96)

• The subject must be queried to assess compliance with a minimum of a 10 h fast prior to blood draw to ensure the FPG values can be accurately determined. Only water is

permitted. If a subject has not fasted for 10 h, the subject should return within a week after proper fasting.

- Diary and SMBG review
- Physical examination
- Vital Signs: blood pressure, pulse, temperature, respiratory rate taken in the sitting position after at least 5 minutes of rest. Blood pressure must be measured twice with at least 3 min apart
- 12 lead ECG taken in the supine position after at least 5 minutes of rest
- Blood draw for hematology (CBC with platelets, WBC with differential), serum chemistry including FPG, and coagulation as detailed in section 6.7.1
- Urinalysis
- Collect plasma sample for drug exposure verification
- Assess adverse events and record concomitant medications

7.3.7 Visit 15 – Exit Visit (week 97)

Follow-up is planned at approximately one week after the last dose is administered. If subjects have an ongoing adverse event, the subject will be followed until the adverse event is resolved or returns to baseline. All possible attempts will be made to document resolution of acute and chronic toxicities. Diary and SMBG review

- Physical examination
- Vital Signs: blood pressure, pulse, temperature, respiratory rate taken in the sitting position after at least 5 minutes of rest. Blood pressure must be measured twice with at least 3 min apart
- 12 lead ECG taken in the supine position after at least 5 minutes of rest
- Blood draw for hematology (CBC with platelets, WBC with differential), serum chemistry including FPG, and coagulation as detailed in section 6.7.1
- Urinalysis
- Assess adverse events and record concomitant medications

7.4 Early Termination Procedures

Subjects removed from study due to drug related toxicity will be followed until resolution or stabilization of the adverse event. Sponsor must be notified in the event that a subject withdraws or is withdrawn from the study.

Subjects who withdraw consent and have received study drug will have a follow-up examination, including a complete physical examination, vital signs, ECG, CBC, urinalysis, and serum chemistry tests.

8 QUALITY CONTROL AND ASSURANCE

The clinical research facility will be monitored by the study monitor to ensure correct performance of the study procedures and assure that the study will be conducted according to the protocol and relevant regulatory requirements. CRF entries will be verified with the source documentation.

Quality control principles will be applied throughout the performance of this study by following the SOPs of the CRO and the sponsor. Review procedures will be implemented at the CRO for all documents that are generated in relation to the study.

9 PLANNED STATISTICAL METHODS

9.1 General Considerations

The primary objective of this trial is to assess the efficacy of EGT0001442 in treatment-naïve type-2 diabetic patients or patients on a single oral anti-diabetic drug in combination with diet and exercise with an HbA1c between 7 and 10%. Efficacy, in this case, is defined as a significant reduction in HbA1c at week 24 when compared to placebo. The effect of EGT0001442 on fasting glucose, blood pressure, body weight and the general safety of EGT0001442 in patients with T2DM will also be explored.

Statistical analyses and summaries of safety and tolerability will be performed using SAS® software (SAS Institute, Cary, NC). In all cases, significance will be judged at the α =0.05 level. No multiplicity adjustment will be required for the single primary endpoint.

9.1.1 Handling Dropouts, Multiples, Missing Data, and Outliers

Discontinuation criteria are explained in Section 6.11. Patients who discontinue will not be replaced. Data will be evaluated for any bias in the pattern of missing data prior to inference testing. Absence of a discernable pattern will be taken as a reliable indication that the incidences of missing data are random occurrences and will not be addressed further. Clinically relevant patterns of missing data will be summarized in the Clinical Trial Report and summarized as notes to any affected tables and listings. Missing data will not be imputed and the observation for that subject will be effectively deleted for that subject.

9.1.2 Multiple Comparisons / Multiplicity

There is a single primary endpoint in this study and no correction for multiple comparisons is needed. Important secondary endpoints are considered exploratory and will not be corrected.

9.2 Determination of Sample Size

Approximately 300 patients will be enrolled and equitably allocated to receive either 20 mg/day EGT0001442 or placebo.

The sample size of 150 subjects per group was calculated based on the following assumptions:

- 1. This effect size is the mean difference between baseline and week 24. The active doses will decrease the HbA1c by 0.4%.
- 2. The placebo will not experience a substantive average decrease in mean HbA1c from baseline to week 24
- 3. The standard deviation of this difference is the same for both groups and is 1.0%.
- 4. The study design is balanced and the two-sided significance level for the hypothesis is 0.05.

Under the above assumptions, an evaluable sample size of 131 evaluable patients per treatment arm yields approximately 90% power that EGT0001442 treatment will be found to be significantly different from placebo. A sample size of 150 subjects per treatment arm will be enrolled to account for any subject lost-to-follow-up.

9.3 Analysis Populations

This study will be conducted at multiple investigative sites and will likely involve variable numbers of subjects at each site. Enrollment will be on a competitive basis but will be capped at 90 subjects in one center.

All patients in the Intent-to-Treatment (ITT) sample will be analyzed according to the treatment they were randomized to receive, and not according to what they actually received, if different. All efficacy analyses will be performed on the ITT sample. All patients in the Per Protocol (PP) sample will be analyzed according to the treatment actually received, and not according to the treatment they were randomized to receive, in the event there is a discrepancy. The analyses of primary efficacy endpoint and selected secondary efficacy endpoints will be performed on the PP sample. The Safety sample will include all randomized patients who have received study drug. The safety sample will be used for safety analysis.

9.4 Demographics and Baseline Characteristics

Patients must meet all inclusion criteria and none of the exclusion criteria in order to participate in the study. Demographic characteristics include age, gender, race, ethnicity, and study center. Baseline characteristics include baseline HbA1c values, blood pressure, Body Mass Index (BMI in kg/m²), whether treatment naïve or not. Summary descriptive statistics will include counts and percentages for discrete variables and estimation of means, standard deviations, medians, inter-quartile range, minimum and maximum for continuous metrics.

9.5 Analysis of Efficacy

Efficacy data includes HbA1c, FPG, body weight, systolic and diastolic blood pressure, and % of subject who achieve HbA1c <7% at week 24. Observed data will be summarized as counts and percentages for discrete variables and estimation of means, standard deviations, medians, inter-quartile range, minimum and maximum for continuous metrics. All data will be presented in by-subject listings and included in the clinical trial report.

9.5.1 Primary Efficacy Endpoint

The primary hypothesis is that EGT0001442 reduces HbA1c after 24 weeks of treatment when compared to placebo controls. Change in HbA1c will be estimated as HbA1c at 24 weeks minus HbA1c at baseline. The two groups will be compared with a t-test at a significance level of 0.05. For subjects that receive rescue medication due to hyperglycemia, the last HbA1c prior to receiving rescue medication will be carried forward to week 24.

9.5.2 Secondary Efficacy Endpoints

The secondary endpoints are considered exploratory and will not be corrected for multiplicity. The first secondary hypothesis is that EGT0001442 reduces FPG at weeks 2 and 24 when compared to controls. Change in FPG for each follow up visit will be estimated as follow-up minus baseline and the two treatment groups will be compared with two paired t-tests.

The second hypothesis is that EGT0001442 reduces the HbA1c to less that 7% of more patients when compared to placebo. HbA1c categories will be assessed for each patient as <7% or \geq 7% of each subject. The 2x2 contingency table of treatment by HbA1c category will be analyzed with a χ^2 test.

The third hypothesis is that EGT0001442 reduces blood pressure compared to placebo. Systolic and Diastolic blood pressure will be measured at baseline and at weeks 2 and weeks 24. Change in each blood pressure metric for both follow up visits will be estimated as follow-up minus baseline and the two treatment groups will be compared with four paired t-tests.

The fourth hypothesis is that EGT0001442 reduces body weight compared to placebo. Body weight will be measured at baseline and at weeks 2 and weeks 24. Change in body weight for both follow up visits will be estimated as follow-up minus baseline and the two treatment groups will be compared with two paired t-tests.

The final secondary hypothesis is that EGT0001442 induced change in HbA1c is evident over time, present at week 24 and maintained over the 96 weeks of the study. HbA1c is collected at baseline and weeks 2, 6, 12, 24, 36, 48, 60, 72, 84 and 96. Repeated measures of HbA1c will be analyzed with a linear mixed effect model to assess the overall treatment effect. Subsequently the change in each time point will be estimated as described for the primary endpoint and evaluated with 10 t-tests.

9.5.3 Additional Efficacy Endpoints

As with HbA1c, repeated measures are available for body weight, systolic and diastolic blood pressure, and fasting plasma glucose. Repeated measures of these variables will be analyzed individually with a linear mixed effect model to assess the overall treatment effect. Subsequently the change in each time point will be estimated as described for the primary endpoint and evaluated with t-tests.

The effect of demographic covariates such as gender, race, age, treatment center, will be evaluated on the primary endpoint and selected secondary endpoints (FPG, blood pressure, and body weight) using Analysis of Covariance. Demographic variables will be included in the model of change in the dependent variable with treatment.

9.6 Analysis of Safety

Safety data includes adverse events (AEs), physical exam results, vital signs, ECG results, and clinical lab results including serum chemistry, hematology, and urinalysis. Observed data will be described as counts and percentages for discrete variables and estimation of means, standard deviations, medians, inter-quartile range, minimum and maximum for continuous metrics. All patients will be included in the safety analysis. All safety data will be presented in by-subject listings and included in the clinical trial report.

9.6.1 Adverse Events

Adverse events will be mapped to preferred term and body system using the Medical Dictionary for Regulatory Activities (MedDRA) dictionary. The number and percentage of patients reporting adverse events will be determined by relationship to treatment and by severity of the event. Drug-related adverse events will be considered those to be at least possibly related to EGT0001442 administration.

Adverse event listings will be provided for the following subsets:

- All treatment emergent AEs (TEAEs)
- All TEAEs at least possibly related to EGT0001442
- Serious TEAEs (if any)
- TEAEs leading to study discontinuation (if any)

AEs are treatment emergent if occurring on or after EGT0001442 administration. TEAEs will be considered at least possibly related to EGT0001442 based on the investigators assessment. Only TEAEs will be tabulated in summary tables.

Tabulations will display TEAEs by severity, and relationship to EGT0001442.

9.6.2 Adverse event of special interest

9.6.2.1 Genitourinary infections

Genitourinary infections as defined in Section 6.9.7.1 will be summarized. Event terms, signs, symptoms, infectious agent (bacterial or fungal), and treatment undertaken will be documented in the listing.

9.6.2.2 Major Adverse Cardiovascular Event (MACE)

All events that potentially represent myocardial infarction, cerebrovascular accident (stroke), acute coronary syndrome, or cardiovascular death are to be evaluated by an independent adjudication committee. There will not be any analysis performed.

9.6.2.3 Hypoglycemia

Severe hypoglycemia as defined in Section 6.9.7.3 will be presented in a listing and summarized.

9.6.2.4 Renal and Urinary disorders

Events as defined in Section 6.9.7.1 will be summarized. Event terms, signs, and symptoms will be documented in the listing.

9.6.3 Clinical and Laboratory Events and Analyses

Clinical and laboratory metrics are measured at baseline and weeks 2, 6, 12 and 24 during the study. During the treatment extension they are measured every 12 weeks up to a total of 96 weeks. These variables include vital signs (blood pressure, respiration, and temperature), Clinical laboratory (see section 6.7 for a complete list) and ECGs.

Laboratory data will be summarized using Low-Normal-High shift tables. ECG results will be summarized as changes from baseline in intervals. Abnormalities as well as changes from previous assessment will be listed.

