After the run-in period, approximately 300 subjects will complete the baseline assessment on day 1 after overnight fasting to confirm their eligibility. The subjects that remain eligible will be randomly assigned to one of the 2 treatment groups on day 1. Randomization will be stratified by study center and based on screening HbA1c (\geq 7 to <8.5% or \geq 8.5 to 10%). The planned doses are 30 mg/day of EGT0001442 or placebo. Each subject will be provided with study drug for 6 weeks, dosing instructions and log, diet and exercise counseling, and a diary card for recording food and fasting glucose information on the days prior to each clinic visit.

Each subject will be instructed to return to the clinic on weeks 2, 6, 12, 18, and 24 for safety monitoring and efficacy assessment including review of adverse events, concomitant medication, ECG, vital signs, physical examinations, testing of blood chemistry and hematology laboratory parameters, and a urinalysis.

Subjects who complete the 24-week treatment period will continue receiving the study drug for an additional 72 weeks. Subjects who receive rescue medication due to poor glycemic

control will continue to receive approved anti-diabetic medications and standard of care per investigator decision according to current treatment guidelines for 72 weeks. In the treatment extension period, subjects must return to the clinic on weeks 36, 48, 60, 72, 84, and 96 for continuous safety monitoring and efficacy assessment, including review of HbA1c values, adverse events, concomitant medication, ECG, vital signs, and physical examinations. A follow up exit visit will be conducted at 1 week after the last dose. Subjects will be advised to see their primary physician and resume standard of treatment to control diabetes.

GLYCEMIC CONTROL

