6.5 Electrocardiography

A 12-lead electrocardiogram (ECG) will be conducted as listed in study activity chart in Appendix 1 and whenever clinically indicated.

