  - V8-V15 and ET: CBC, electrolytes, BUN, creatinine, Lipids (TG, TC, HDL-c), ALT, AST, bilirubin (total and direct), HbA1c, FPG. PT only at V8, and V15 or ET.
-  Clean catch sample to be collected at each visit and sent to the central lab. Urine drug screen on screening (visit 1). On-site urine dipstick to be performed at all visits except V2.
- NMP22 testing will be performed at screening (V1), randomization (V3), and at weeks 24 (V8), 48 (V10), 72 (V12), and 96 (V14) or when clinically indicated. For subjects who do not have baseline NMP22 testing following Protocol Amendment 1 (11 April, 2011), NMP22 testing will be performed in the next visit or within 4 weeks after Amendment is approved, whichever comes first.
- Adverse events of special interest are specified to be:
  - Cardio- and cerebro- vascular events,
  - Genitourinary infections
  - Increase in creatinine from baseline by 0.5 mg/dL or more
  - Increase in ALT, AST or bilirubin to >3x ULN
- Visit to be conducted one week after last dose of study drug whether subject early terminates from study or completes V14.

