### See table 14.3-2.4 for layout. Use footnotes below.

Note: Baseline is defined as the last available assessment on or prior to the first dose of study medication. The number of subjects with a value at baseline and at the specified visit is displayed.

Source Data: Listing 16.2-9.3

Programming note: use all available timepoints per data following order such as Baseline, Week 2, 6, 12, 18, 24, 36, 48, 60, 72, 84, 96, 97 and 1 week follow-up.

Protocol: THR-1442-C-418 Page x of y

Table 14.3-3.1 Change from Baseline in Vital Signs (Safety Analysis Set)

See table 14.3-2.1 for layout. Use footnote below.

Note: Baseline is defined as the last available assessment on or prior to the first dose of study medication. Source Data: Listing 16.2-10.1

Programming note: use timepoints of Baseline, Week 2, 6, 12, 18, 24, 36, 48, 60, 72, 84, 96, 97 and 1 week follow-up. Use the following parameters: Pulse, Temprature and Respiration Rate (3 parameters).

Table 14.3-4.1 Change from Baseline in ECG Values (Safety Analysis Set)

See table 14.3-2.1 for layout. Use footnote below.

Note: Baseline is defined as the last available assessment on or prior to the first dose of study medication. Source Data: Listing 16.2-10.2

Programming note: use timepoints of Baseline, Week 24, 60, 96, 97 and 1 week follow-up.

Table 14.3-4.2

Overall ECG Interpretations and Abnormal Findings (Safety Analysis Set)

Visit	EGT0001442	Placebo
Assessment	(N=xxx)	(N=xxx)
Screening		
n	xxx	xxx
Normal	xxx (xx.x%)	xxx (xx.x%)
Abormal	xxx (xx.x%)	xxx (xx.x%)
Clinically Significant	xxx (xx.x%)	xxx (xx.x%)
Not Clinically Significant	xxx (xx.x%)	xxx (xx.x%)
Missing	xxx (xx.x%)	xxx (xx.x%)
Week 0		
n	xxx	xxx
Normal	xxx (xx.x%)	xxx (xx.x%)
Abormal	xxx (xx.x%)	xxx (xx.x%)
Clinically Significant	xxx (xx.x%)	xxx (xx.x%)
Not Clinically Significant	xxx (xx.x%)	xxx (xx.x%)
Missing	xxx (xx.x%)	xxx (xx.x%)

Source Data: Listing 16.2-10.3

Programming note: use all available timepoints per data following order such as Screening, Week 0, 24, 60, 96, 97 and 1 week follow-up.

Table 14.3-4.3
ECG Results by Category and Visit
(Safety Analysis Set)

Parameter Visit		0001442 =xxx)		acebo	
ATRIC	( IN	=xxx)	(IV	(=xxx)	
QT Range (msec)					
Week -5					
n		xxx		xxx	
< 450	xxx	(xx.x%)	xxx	(xx.x%)	
>= 450 - < 480	xxx	(xx.x%)	xxx	(xx.x%)	
>= 480 - < 500	xxx	(xx.x%)	xxx	(xx.x%)	
>= 500	xxx	(xx.x%)	xxx	(xx.x%)	
Week 0					
n		xxx		xxx	
< 450	~~~	(xx.x%)		(xx.x%)	
>= 450 - < 480		(xx.x%)		(xx.x%)	

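### ECG timing is stated two ways, no on-drug ECG is scheduled before Week 24, and the SAP visit windows can count a post-treatment ECG under an on-treatment visit

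*Protocol*

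**What the plan says.** **Texts that imply frequent ECGs.** Protocol 9.6.3 states "Clinical and laboratory metrics are measured at baseline and weeks 2, 6, 12 and 24 during the study" and then "During the treatment extension they are measured every 12 weeks up to a total of 96 weeks". It defines the metrics so as to include "Clinical laboratory (see section 6.7 for a complete list) and ECGs". Protocol 3.1 has subjects return on "weeks 2, 6, 12, 18, and 24 for safety monitoring and efficacy assessment including review of adverse events, concomitant medication, ECG, vital signs", and it also names ECG for the six extension visits. SAP 3.1 repeats both lists.

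**Texts that schedule few ECGs.** Protocol 6.5 says a 12-lead ECG "will be conducted as listed in study activity chart in Appendix 1 and whenever clinically indicated". The ECG row of Appendix 1 is marked at screening, Week 0, Weeks 24, 60 and 96, and early termination. The Section 7 visit lists agree and add an ECG at the Week 97 exit visit. SAP Table 1 has the same pattern, with Visit 15 in the last column. The shell for SAP Table 14.3-4.1 says "use timepoints of Baseline, Week 24, 60, 96, 97 and 1 week follow-up".

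**Early leavers.** Protocol 7.4 requires an ECG for dosed subjects who withdraw consent, without saying when. SAP Table 1 describes Visit 15 as "Visit to be conducted one week after last dose of study drug whether subject early terminates from study or completes V14".

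**Slotting.** SAP 5.4.2 assigns every record, early-withdrawal records included, to an analysis visit by study day. In SAP Table 2 the one-week follow-up has a target of last dose plus 7 days, but its interval covers only days later than that.

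**The concern.** A reader of the design or safety-analysis sections would expect four or five ECGs on drug by Week 24. The schedule provides one, at Week 24 itself.

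Two things follow for the analysis. First, a subject who stops before Week 24 may contribute no ECG taken on treatment, and nothing in SAP 9.4 would show how many such subjects there are. Second, the windows can label an ECG taken after dosing ended with an on-treatment visit. The QT category counts, and the Week 24 change from baseline, would then mix on-drug and off-drug recordings without any flag.

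**Working it through.** No stated figure needs reproducing. The check is a count of visits followed by a walk through the windows.

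**1. Scheduled ECGs against described ECGs**

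| Source | On-treatment ECG weeks | Count |
|---|---|---|
| Protocol 9.6.3 | 2, 6, 12, 24, then 36, 48, 60, 72, 84, 96 | 4 + 6 = 10 |
| Protocol 3.1, SAP 3.1 (if read literally) | 2, 6, 12, 18, 24, then 36, 48, 60, 72, 84, 96 | 5 + 6 = 11 |
| Appendix 1, Section 7, SAP Table 1 | 24, 60, 96 | 3 |

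The weeks in 9.6.3 with no scheduled ECG are 2, 6, 12, 36, 48, 72 and 84, which is 10 − 3 = 7. The number scheduled after Week 0 and before Week 24 is 0.

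This is not simply a difference between a February 2011 protocol and a November 2011 SAP. Protocol 9.6.3 disagrees with protocol Appendix 1, and SAP 3.1 disagrees with SAP Table 1, each within one document.

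**2. Where an on-target follow-up ECG lands**

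Let L be the study day of last dose. The on-target ECG is on day L + 7. The follow-up interval requires a day later than L + 7, so the target day fails it. The record then goes wherever its study day falls:

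- L = 145: the ECG is on Day 152, inside Week 24 (Days 149 to 211). Week 24 is a scheduled ECG visit, so the value is summarized as Week 24, seven days after dosing stopped.
- More generally, L + 7 lies in the Week 24 window when L is between 149 − 7 = 142 and 211 − 7 = 204. Subjects who stop on Days 142 to 168 have not reached the Week 24 target day (169).
- L = 70: the ECG is on Day 77, inside Week 12 (Days 65 to 106). ECG is not scheduled then. SAP 5.4.2 leaves such values out of by-visit summaries, except summaries focusing on extreme values. The shell for Table 14.3-4.3 uses all time points available in the data, so the value could appear there as Week 12.
- L = 673 (a completer on target): the ECG is on Day 680. The Week 96 window closes at last dose and the Week 97 interval needs a day after 680, so the record has no slot.

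**3. One day late**

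With L = 145 and the ECG on Day 153, the record satisfies both the follow-up interval (later than Day 152) and the Week 24 window. The SAP does not say which takes precedence, so moving the boundary by one day is not enough by itself.

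**The case against.** The strongest reply is that site conduct is not in doubt. Protocol 6.5 expressly makes Appendix 1 the source for ECG timing, and Appendix 1, the Section 7 visit lists and SAP Table 1 agree on the on-treatment visits. Protocol 3.1 is a collective list: it also names physical examinations for Weeks 2 to 24, which Appendix 1 places only at Weeks 12 and 24. The 11-visit reading is therefore weak. Section 9.6.3 is loose elsewhere too, since it omits Week 18 although laboratory tests and vital signs are scheduled then. All of this stands, and it makes the reconciliation close to clerical.

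A reader might infer that early leavers have no ECG after baseline. The documents do not support that: Appendix 1 marks an ECG at early termination, protocol 7.4 requires one for dosed subjects who withdraw consent, and SAP Visit 15 covers early terminators. Anyone leaving after the Week 24 visit also has that visit's ECG.

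A reader might also infer that the QT summaries cannot show any effect in the first 24 weeks. That goes too far. Clinically indicated ECGs are allowed at any time, and Tables 14.3-4.2 and 14.3-4.3 take all available time points.

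Finally, Table 14.3-4.3 is laid out by visit, with Week 97 and the one-week follow-up as separate rows. That answers part of the slotting concern, but only for records that reach those rows. Under the Table 2 interval, an on-target record does not.

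**Conclusion.** The point holds as a minor one. The texts describe 10 on-treatment ECG time points in one place and schedule 3 in another, with none fixed between baseline and the Week 24 visit. For subjects who stop before Week 24, the defensible statement is that they may have no on-drug ECG. It rests on the SAP timing of Visit 15 and on the protocol's silence about when the early-termination ECG is taken relative to last dose.

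The slotting fault can change a tabulated result. It follows from Table 2 as written and assumes only that the follow-up ECG is taken on or near its target day. How many subjects it would affect cannot be computed, because the documents give no rate or timing of early withdrawal. Whether ECGs before Week 24 are needed is for the sponsor to decide.

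**What to change.** - **One schedule.** Reconcile protocol 3.1, 9.6.3 and Appendix 1 with SAP 3.1 and SAP Table 1. The sponsor decides which schedule was intended. The Section 7 visit lists and the ECG shells should then match it.
- **Follow-up window.** In SAP Table 2, make the Week 97 and one-week follow-up intervals include their target day, and state that a post-treatment follow-up record takes precedence over the study-day windows.
- **QT tables.** In SAP 9.4 and Table 14.3-4.3, keep ECGs from the post-treatment follow-up out of the on-treatment visit counts.
- **Reporting.** Add one line giving the number of subjects per arm with no on-drug ECG.

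The cost is wording in both documents, a corrected interval and precedence rule in Table 2, and one extra table row. Additional ECGs would be a cost only if the sponsor decides that the fuller schedule was meant.
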